8.4 Minimization of Risks

8.4.1 Although the risks outlined in Section 8.1 may occur, the likelihood of serious events occurring is considered minimal. Carl Zeiss, Inc. has reduced the potential of the above risks by:

- Performing complete validation testing of the Intrabeam PRS
- Implementing quality assurance measures each day prior to using the Intrabeam PRS
- Providing adequate directions for use in device labeling.

Clinical investigators who are involved in the study are knowledgeable and experienced in the field of surgical oncology and radiation oncology, which will help to minimize risks to the patients involved. Inclusion/Exclusion criteria are intended to reduce the potential of including patients who might be prone to injury or who might be inappropriate candidates of IORT for other reasons.

8.4.2 Potential Patient Benefits

- a. The potential benefits of IORT are:
- b. Decreased likelihood of tumor recurrence
- c. More accurate delivery of radiation dose to targeted tissue
- d. Reduced radiation delivered to normal breast and surrounding tissues
- e. Reduced delays in systemic/local therapy
- f. Reduced risk of infection and skin toxicity compared to standard external beam or other partial breast irradiation techniques
- g. Reduced treatment time Improved patient compliance
- h. Possibly increased feasibility of breast conserving therapy

9.0 CLINICAL AND LABORATORY EVALUATIONS AND STUDY CALENDAR

- 9.1 Histological Evaluation of Specimen. The surgical specimen will undergo histological evaluation to determine the following features: DCIS histology, lesion size, surgical margin width, and the presence or absence of invasive carcinoma. The surgical margin width will be measured as distance from the nearest tumor cell to the cut or inked edge of the WLE surgical specimen.
- 9.2 DCIS histology [histologic type, grade (nuclear, histologic, mitotic), and the presence or absence of comedonecrosis] will be determined using the Philadelphia consensus guidelines (Appendix 1) and assessed in the core biopsy and/or WLE specimen prior to administration of IORT. In addition, The Van Nuys Prognostic Index (VNPI) score will be calculated and reported in the final WLE specimen (Appendix 2).
- 9.3 Surgical margin width will be measured in all directions (i.e., superior, inferior, medial, lateral, anterior and posterior) in the WLE specimen. The anterior and posterior margins will be considered widely clear if the involved margin(s) approximate the skin (anterior) or pectoralis fascia (posterior) AND these margins have been removed with the surgical specimen.
- 9.4 DCIS lesion diameter will be measured in the three widest dimensions (e.g., anterior-posterior diameter, medial-lateral diameter, superior-inferior diameter) in the WLE specimen. Specimen weight will also be recorded.

9.5 Study Calendar.

Data Required	Pre-Entry	Surgery/ Applicator Placement	Post Surgery	Follow up
Demographics/Medical History	X			
Inclusion/Exclusion (Eligibility) (TT01*)	X		X	
Mammography (TT02)	X ^b			X ^b ,
CE-MRI (TT02)	X ^d			X ^d
Pathology (TT06)	X		X	
Intrabeam PRS Placement, Brachytherapy & Removal (TT04, TT10, TT07)		X		
Follow-Up Visit (TT11, TT12, TT05, TT13)				X _a ,
Quality of Life Questionnaires (EORTC QLQ-BR23 & QLQ-C30 version 3.)				X ^f
Photographs				X ^c
Cosmesis				X ^e
Adverse Event Reporting at each visit (TT09)		X	X	X

*TT refers to the respective data collection form (see Section 12.0).

- a. The patient will be evaluated at 3 months, 6 months, 1 year, and 2 years post-IORT.
- b. Mammograms of the treated breast will be performed at baseline within 60 days of accrual and repeated semiannually post_IORT X 2 years
Suspected recurrences and new cancers detected using imaging and/or physical examination will be confirmed histologically.
- c. Photos of both breasts will be obtained at 3 months, 6 months, 1 year, and 2 years post-IORT. The first photo will be taken of both breasts with the patient standing with both arms at her side. The second photo will be taken of both

breasts with the patient standing with her hands on her hips. Care will be taken to exclude the patient's face from the photo.

- d. MRI will be performed at baseline within 60 days of accrual. MRI may also be performed at any time to evaluate a clinical or mammographic finding or to follow-up on an earlier MRI finding.
- e. Cosmesis will be reported at 3 months, 6 months, 1 year, and 2 years post-IORT.
- f. Quality of life will be evaluated at baseline (preoperatively), 3 months, 6 months, 1 year, and 2 years post-IORT.

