3.2.2 Rationale for Inclusion of Cohort 2. Although mammography is the standard imaging tool used for the detection and pre-operative staging of DCIS, the extent of the imaging abnormality may not always correspond exactly to the extent of DCIS within the breast. CE-MRI may enhance the radiologist's ability to evaluate the extent of disease within the breast. However, since CE-MRI is typically performed after a core biopsy has already established the diagnosis of DCIS, post-biopsy artifact may lead to over-estimation of lesion size. Given these limitations of imaging, one reason that Cohort 2 has been included is to preserve the option of IORT for patients who may have been excluded from immediate IORT based on imaging or clinical findings but who were ultimately found to be suitable candidates based on surgical pathology. In addition, Cohort 2 also provides an opportunity to examine the safety and tolerability of administering delayed IORT after an initial WLE. Given the limited availability of IORT nationwide, establishing the safety and tolerability of delayed IORT as adjuvant therapy for DCIS is particularly important to referral centers interested in offering IORT to women who have already undergone successful or unsuccessful WLE at another facility, but who now present for definitive care.

3.2.3 Rationale for Inclusion of Cohort 3. Despite pre-operative mammograms and CE-MRI showing localized DCIS ≤ 4 cm, it is expected that a minority of patients will be found to be unsuitable candidates for IORT on the basis of extensive multifocal or multicentric carcinoma. The rationale for including these patients in the study is to examine the safety and tolerability of breast cancer treatment [e.g., WB-EBRT (with or without re-excision) or mastectomy] in patients who have previously received IORT. Comparison of the preoperative imaging findings and surgical pathology results should ultimately improve our ability to identify pre-operatively these unsuitable candidates for immediate IORT.

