5.3.2 Cohort 1 (Immediate IORT group)

- a. Localized DCIS measuring ≤ 4 cm on preoperative imaging.

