7.0 STUDY AGENT ADMINISTRATIONS OR INTERVENTION AND TOXICITY MANAGEMENT PLAN

7.1 Patient Surgery and IORT

- 7.1.1 Each patient will undergo WLE to remove DCIS and to create a cavity. Each of the following procedures qualifies as WLE: breast conserving surgery, lumpectomy, segmental mastectomy, segmental resection, and partial mastectomy.
- 7.1.2 Recognizing the potential for DCIS to be larger than demonstrated on imaging, the surgeon will aim to excise the lesion with surgical margins of 10 mm. Multiple localizing wires will be placed pre-operatively to facilitate resection.
- 7.1.3 Due to the potential for finding occult microinvasive carcinoma in the final surgical pathology, sentinel node biopsy will be allowed at the discretion of

the surgeon.

- 7.1.4 At the conclusion of IORT, surgical clips will be placed in the resection cavity to mark the surgical margins to facilitate re-excision, if indicated.
- 7.2 Criteria for Receiving Additional therapy after IORT (Cohort 3)
 - 7.2.1 Patients with DCIS >5 cm will be advised to undergo WB-EBRT (or mastectomy) despite having received IORT, even if surgical margins are clear (\geq 2mm).
 - 7.2.2 Patients with surgical margins width of <2 mm following local excision and immediate IORT will be advised to undergo re-excision. If residual disease is found and new final margins are <2 mm, the patient will be advised to undergo WB-EBRT. However, no addition therapy will be needed if no residual disease is found, or if final margins is \geq 2mm.

7.3 Ancillary treatments.

Neoadjuvant hormonal therapy (e.g., Tamoxifen or Fulvestrant) and chemopreventive therapy (e.g., green tea extract) will be allowed provided that the total duration of neoadjuvant hormonal or chemopreventive therapy does not exceed 30 days prior to WLE and immediate IORT.

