10.0 CRITERIA FOR EVALUATION AND ENDPOINT DEFINITIONS

10.1 Feasibility Endpoint. The primary efficacy endpoint of the treatment will be re-operation (re-excision or mastectomy) rates following WLE and IORT.

Re-excision (or mastectomy) will be indicated for patients with microscopic surgical margins measuring <1 mm following WLE and immediate IORT.

Additionally, the following data will also be reported and analyzed:

10.1.1 Indications for WB-EBRT. Patients with margins that are margins < 2 mm after reexcision for <2 mm margins, or, DCIS > 5 cm.

10.1.2 Extent of disease. Extent of disease will be determined by measuring the dimensions of the DCIS lesion as demonstrated by pre-operative mammography and CE-MRI and the dimensions of the DCIS lesion contained within the surgical resection specimen

10.1.3 Surgical Margins. Surgical margins will be defined as the distance from the closest tumor cells to the cut or inked edge of the surgical specimen.

10.1.4 DCIS histopathology. DCIS histopathology will be determined by evaluating the histopathological type, grade (histological, nuclear, and mitotic), the presence or absence of comedonecrosis or invasive carcinoma in the pre-operative biopsy and the surgical specimen.

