13.1 Study Design and Sample Size Justification

The study design was selected based on the primary aim: to evaluate the ability of CE-MRI and mammography to identify patients for whom IORT is not optimal because of the inability to achieve sufficiently wide surgical margins. If 15% or fewer patients require re-excision, this would be considered acceptable and encouraging for further study; however, a reexcision rate of 30% or higher would not be acceptable.

13.1.1 Accrual to Cohort 1 (Specific Aims 1-3 in Sections 2.1 – 2.3).

Patients will be enrolled in Cohort 1 until 79 patients have received immediate IORT. All patients who are deemed eligible for IORT based on mammography and CE-MRI results will be considered in the decision to stop or continue the trial. There will be one interim analysis when 25 patients have completed WLE and immediate IORT, whether or not additional therapy is needed.

After 25 patients have been evaluated, if 19 or more did NOT require re-excision (based on the surgical specimen), then accrual will continue until 79 patients undergo WLE and immediate IORT. If 7 or more of the initial 25 needed re-excision, then the study will terminate and investigators will conclude that the current method for staging is not sufficiently accurate.

After 79 patients have been evaluated, if 62 or more did NOT need re-excision (based on surgical specimen), investigators will conclude that the chance of correctly identifying a tumor that is suitable for IORT is greater than 70% and that further study of the approach would be justified. If 18 or more of the initial 79 needed re-excision, then investigators will conclude that the chances of correctly identifying a tumor that is suitable for IORT is less than 85%. In this instance, investigators would aim to improve the staging procedures before continuing with this approach.

With this Simon optimal 2-stage design, there will be a 5% chance (alpha) of incorrectly deciding that that approach warrants further study, when the true chance of correctly staging is less than 85%; and there will be a 10% chance (beta) of correctly deciding that this approach warrants further study, when the true chance of correctly staging is greater than 70%.

To evaluate the safety and tolerability of immediate IORT, the following side effects or complications will be taken as evidence that IORT was not well tolerated:

- a. any Grade 2 or greater toxicity

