13.2 Analysis of Results

The outcome of all patients who are registered onto this study will be reported. The results of patients in Cohorts 1, 2, and 3, will be summarized separately.

For those patients whose CE-MRI and mammography results suggested that they would be candidates for IORT (i.e. Cohort 1), the surgery results will be summarized in terms of whether or not a re-operation was indicated (because of inadequate margins or for any other reason) or whether or not WB-EBRT was recommended (because of small margin size or large tumor size, or another reason). For those patients who subsequently underwent re-excision +/- WB-EBRT or who subsequently received WB-EBRT alone (or mastectomy), all complications and side effects will be summarized.

For all patients, the size of the lesion as estimated by the imaging modalities will be compared to the size measured in the surgical specimen.

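### Reference lesion size is taken from the first excision, so in re-operated patients with residual DCIS it is a lower bound and the size comparison understates how far imaging fell short

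*Combined protocol and SAP*

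**What the plan says.** The measuring rule is in Section 9.4: "DCIS lesion diameter will be measured in the three widest dimensions (e.g., anterior-posterior diameter, medial-lateral diameter, superior-inferior diameter) in the WLE specimen". Section 10.1.2 defines pathological extent as "the dimensions of the DCIS lesion contained within the surgical resection specimen". Section 13.2 plans, for all patients, that "the size of the lesion as estimated by the imaging modalities will be compared to the size measured in the surgical specimen". Both of these refer to one specimen. In Section 13.1.1 the same term means the specimen that decides whether a re-excision is needed, since accrual continues "if 19 or more did NOT require re-excision (based on the surgical specimen"; that can only be the first WLE.

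For the re-excision specimen, Section 7.2.2 uses residual disease and the new margins: "If residual disease is found and new final margins are <2 mm, the patient will be advised to undergo WB-EBRT". It records no size, and no section says how to combine extents across specimens.

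The comparison has a stated purpose. Section 3.1 uses it to evaluate how well imaging selects candidates. Section 3.2.3, on patients who need further treatment after IORT, says: "Comparison of the preoperative imaging findings and surgical pathology results should ultimately improve our ability to identify pre-operatively these unsuitable candidates for immediate IORT".

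Some wording is looser. Section 3.2.1 calls a re-excision a repeat WLE, Section 9.2 scores the VNPI in the final WLE specimen, and the opening of Section 13 speaks of surgical specimens in the plural.

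**The concern.** When a lesion has been cut through, the first specimen shows only the part that was removed. Its measured diameter is a minimum. If that minimum enters the comparison as the true size, pathological size can only be too small, so imaging looks closer to pathology than it was.

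The error is not spread evenly. It is zero where the lesion was wholly removed and falls only on patients whose disease ran past the first cut. Those patients lie within the re-operated group that Section 3.2.3 wants to learn to recognise before surgery. At stake is a biased descriptive result, and possibly a wrong lesson about how far imaging falls short when it fails.

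**Working it through.** **1. The plan's own design figures.** The plan states no figure for the size comparison, so the check starts with the Cohort 1 design. The rule is to continue with 19 or more of 25 free of re-excision and to succeed with 62 or more of 79, with success rates of 0.70 (unacceptable) and 0.85 (acceptable).

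P(success | p) = sum over x = 19 to 25 of Bin(x; 25, p) × P(Bin(54, p) ≥ 62 − x)

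This gives 0.0492 at p = 0.70 and 0.904 at p = 0.85, which agrees with alpha 5% and beta 10%. The outcome is re-excision yes or no. Lesion size does not enter, so changing the reference size leaves all of this unchanged.

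**2. Who is affected.** Section 13.1.3 expects 8 to 17 additional procedures among 79 patients: 8/79 = 10.1%, 17/79 = 21.5%. Only those with DCIS beyond the first excision have a truncated size. A close but clear margin with no residual disease gives a correct one.

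**3. What a specimen cut to plan can show.** Section 7.1.2 says "the surgeon will aim to excise the lesion with surgical margins of 10 mm". If the cut is exactly 10 mm beyond the imaged edge on both sides, specimen span = imaged size + 2 × 10 mm. As a constructed single case, take an imaged size of 2.5 cm and a true span of 6.0 cm:
- specimen span = 2.5 + 2.0 = 4.5 cm
- recorded underestimation = 4.5 − 2.5 = 2.0 cm
- true underestimation = 6.0 − 2.5 = 3.5 cm

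**4. Average size of the effect.** The documents give no distribution of imaging error, so these inputs are assumptions: one axis; imaged size uniform from 1 to 4 cm (the upper end from Section 5.3.2, "Localized DCIS measuring ≤ 4 cm on preoperative imaging"); mean true excess 0.3 cm, i.e. 0.15 cm per side; normal error per side; cut at +1 cm per side.

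Recorded size = imaged size + sum over the two sides of min(excess, 1 cm)

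Results for patients with a margin below 2 mm:

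| SD per side | Share with margin <2 mm | Mean true underestimation | Mean recorded | Mean loss | Share truncated |
|---|---|---|---|---|---|
| 0.45 cm | 14% | 1.12 cm | 1.05 cm | 0.7 mm | 41% |
| 0.60 cm | 26% | 1.19 cm | 1.02 cm | 1.6 mm | 58% |
| 0.80 cm | 37% | 1.28 cm | 0.96 cm | 3.2 mm | 72% |

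Dividing mean loss by share truncated gives the loss among lesions actually cut through: about 1.8, 2.8 and 4.4 mm (from unrounded values). Only the first row lies inside the protocol's 10.1% to 21.5%. With the 1 mm trigger of Section 10.1 in place of 2 mm, SDs of 0.50 and 0.55 cm give rates of 13% and 17% and mean losses of 1.4 and 1.8 mm.

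**5. Wider assumptions.** With SDs of 5 to 15 mm, one or three axes, either trigger, and the mean tuned to a 15% or 30% re-operation rate, the mean loss in re-operated patients runs from 0.7 to 7.6 mm, and 38% to 91% of them are truncated. The upper end is hard to reconcile with the plan: an SD of 15 mm gives a 15% rate only if true extent falls on average 12 to 21 mm per side inside the imaged edge. The direction of the bias is the same in every setting.

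**The case against.** The strongest reply has four parts.

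*The WLE-only reading is inferred.* Re-excision is once called a repeat WLE, there is mention of a final WLE specimen and of plural specimens, and Section 12 says the forms are still to be created, with an additional-procedure form among them. This stands in part. But Section 9.4 states a rule, and even a wide reading of WLE leaves out a mastectomy specimen and gives no way to combine two specimens.

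*The failure is recorded elsewhere.* A reader might infer that imaging failures disappear from the trial. The documents do not support that. Re-operation is the primary endpoint, margins are measured in all directions, and residual disease and new margins are assessed at re-excision. The amount of underestimation is understated; its occurrence is not lost.

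*There is no fixed 2 cm ceiling.* A reader might infer that recorded underestimation cannot exceed 2 cm, or that a lesion imaged at 3 cm or less (3 + 2 = 5) can never be recorded above 5 cm. Both need an exactly centred cut at exactly 10 mm. Section 7.1.2 states an aim, and Section 1.2.2 describes intraoperative margin assessment. Nor does every close margin mean that imaging fell short; an off-centre excision can produce one.

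*Aim 2 is hardly touched.* A reader might infer that patients above 5 cm are missed and counted as well selected. In the model the share above 5 cm is 1.5% true against 1.2% recorded at SD 0.45 cm (0.3% × 79 = 0.2 patient) and 3.3% against 2.2% at SD 0.60 cm (1.1% × 79 = 0.9 patient). A truncated lesion reaches the cut edge, so Section 7.2.2 already sends it to re-excision. It does not pass as a success.

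What remains is a small, one-directional error in a descriptive analysis, confined to the subgroup of most interest.

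**Conclusion.** The point holds in a limited form. As written, the plan treats a minimum size as exact in re-operated patients with residual DCIS, and the imaging-pathology comparison in Sections 3.1, 3.2.3 and 13.2 leans toward agreement there. Under the illustrative assumptions the average loss is about 1 to 3 mm in patients with a margin below 2 mm, and toward or below the low end of that at the re-operation rate the protocol expects. Single patients can lose more. These sizes rest on an assumed error distribution and a cut made exactly to plan; the direction needs only that the lesion was cut through. No conclusion about the primary endpoint, the two-stage rule, N = 79, alpha or power follows from this. The change is worth making because it is cheap and concerns the patients the comparison is meant to inform.

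**What to change.** In Sections 9.4, 10.1.2 and 13.2, and for the imaging-pathology size comparison only:

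- Define reference extent as the combined DCIS extent over the WLE specimen and any later re-excision or mastectomy specimen taken because of margins, reconstructed from the oriented specimens.
- Where the specimens cannot be aligned and residual DCIS is found, keep the WLE size, flag it as a lower bound and treat it as right-censored.
- Report the size comparison separately for re-operated patients, with the number of flagged sizes.

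For the >5 cm criterion (Sections 7.2.1 and 10.1.1, and the opening of Section 13), reconcile the passages on which specimen or specimens the size refers to. The treatment rule itself is outside this point and should not change because of it.

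The cost is wording in three sections and one extra field on the pathology form; re-excision specimens are already examined for residual disease and margins. The downside is that an extent pieced together from two specimens is less exact than one measurement, which is why the lower-bound flag and the separate report are needed.

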10.0 CRITERIA FOR EVALUATION AND ENDPOINT DEFINITIONS

10.1 Feasibility Endpoint. The primary efficacy endpoint of the treatment will be re-operation (re-excision or mastectomy) rates following WLE and IORT.

Re-excision (or mastectomy) will be indicated for patients with microscopic surgical margins measuring <1 mm following WLE and immediate IORT.

Additionally, the following data will also be reported and analyzed:

10.1.1 Indications for WB-EBRT. Patients with margins that are margins < 2 mm after reexcision for <2 mm margins, or, DCIS > 5 cm.

10.1.2 Extent of disease. Extent of disease will be determined by measuring the dimensions of the DCIS lesion as demonstrated by pre-operative mammography and CE-MRI and the dimensions of the DCIS lesion contained within the surgical resection specimen

10.1.3 Surgical Margins. Surgical margins will be defined as the distance from the closest tumor cells to the cut or inked edge of the surgical specimen.

10.1.4 DCIS histopathology. DCIS histopathology will be determined by evaluating the histopathological type, grade (histological, nuclear, and mitotic), the presence or absence of comedonecrosis or invasive carcinoma in the pre-operative biopsy and the surgical specimen.

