2.0 OBJECTIVES AND PURPOSE

In this investigation, we will determine whether or not patients with DCIS deemed eligible for “immediate” IORT based on pre-operative mammography and CE-MRI can be successfully treated with IORT without the need for additional therapy due to inadequate surgical margins or large tumor size. To accomplish these objectives, this study has several specific aims:

- 2.1 Specific Aim 1: To evaluate the ability of pre-operative mammography and CE-MRI to select suitable candidates for immediate IORT, without the need for re-excision. At USC, the re-excision rate for DCIS is about 20%, compared to published rates as high as 50%⁵⁻⁷. In this study, with the use of CE-MRI, a re-excision rate of 15% or less will be acceptable and a rate of 30% or more will be unacceptable.
- 2.2 Specific Aim 2: To evaluate the ability of pre-operative mammography and CE-MRI to select suitable candidates for immediate IORT, without the need for additional WB-EBRT.
- 2.3 Specific Aim 3: To evaluate the safety and tolerability of IORT administered at the time of initial WLE (immediate IORT).
- 2.4 Specific Aim 4: To evaluate the safety and tolerability of IORT administered at the time of re-excision in a patient who has previously undergone a lumpectomy (e.g., a patient who has inadequate margins but is still believed to be an acceptable candidate for lumpectomy and radiotherapy, or a patient who has previously undergone successful lumpectomy but who desires IORT as adjuvant radiotherapy).
- 2.5 Specific Aim 5: To evaluate the safely and tolerability of post-operative WB-EBRT or mastectomy given after initial unsuccessful IORT (e.g., a patient who initially received immediate IORT but who was subsequently found to an unsuitable candidate for IORT).

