5.3.3 Cohort 2 (Delayed IORT group)

- a. Localized DCIS measuring ≤ 4 cm or less on surgical pathology

- i. Delayed IORT could be performed for the explicit purpose of administering IORT or performed following re-excision of a previously operated breast to achieve clear surgical margins.
- ii. This cohort includes patients who were excluded from immediate IORT based on pre-operative imaging suggesting ineligibility for immediate IORT, but who are subsequently found to meet histological criteria (localized DCIS ≤ 4 cm and no invasive cancer) for IORT based on surgical pathology.
- iii. Unifocal microinvasive (T1mic or invasive focus ≤ 1 mm in maximal diameter) is allowed following initial WLE if surgical pathology margins were ≥ 2 mm for both the invasive and non-invasive components.
- iv. Delayed IORT must be performed within 3 months of initial WLE.

5.3.4 Cohort 3

- a. Subjects who received IORT at the time of initial WLE but whose surgical pathology indicates the need for further therapy:
 - i. DCIS measuring greater than 5 cm on surgical pathology.
 - b. Surgical margins width < 2 mm.

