13.1.3 Accrual to Cohort 3 (Specific Aim 5 in Section 2.5)

Cohort 3 will be a subset of patients who begin in Cohort 1 (i.e. are deemed candidates for immediate IORT and who receive immediate IORT) but who subsequently are found to require a mastectomy, re-excision alone, re-excision followed by WB-EBRT, or WB-EBRT alone. This cohort will be followed to monitor and document the complications of the mastectomy and WB-EBRT (with or without re-excision) which are performed following IORT. If all 79 patients are enrolled in Cohort 1 (i.e. the study is not stopped early), then we would expect between 8 and 17 patients requiring an additional surgical procedure (mastectomy or re-excision); as soon as 18 patients require an additional surgical procedure, the study will be terminated.

Using the same definition of unacceptable toxicity as above in 13.1.1 for Cohort 1 and in 13.1.2 for Cohort 2 (any Grade 2 or greater toxicity, or failure for the surgical incision to heal as evidenced by wound dehiscence,

wound infection, or skin ulceration), the rules in Table 3 will also be applied to the patients undergoing an additional surgical procedure in Cohort 3. Separately, we will evaluate the tolerability of WB-EBRT following IORT, in the same manner (using Table 3). Unacceptable toxicity of WB-EBRT include any Grade 2 or greater toxicity, skin flap necrosis, skin ulceration, wound dehiscence, or brachial plexopathy.

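### The primary event has two margin thresholds, <1 mm in 10.1 and <2 mm in 7.2.2, and the stopping and final rules do not say which one counts

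*Combined protocol and SAP*

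**What the plan says.** Section 10.1 names the re-operation rate (re-excision or mastectomy) as the primary endpoint and adds: "Re-excision (or mastectomy) will be indicated for patients with microscopic surgical margins measuring <1 mm following WLE and immediate IORT".

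Three other places use a wider margin:

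- Section 7.2.2, the treatment rule after immediate IORT: "Patients with surgical margins width of <2 mm following local excision and immediate IORT will be advised to undergo re-excision".
- Section 5.3.4, which lists the findings that show a need for further therapy: "Surgical margins width < 2 mm".
- Section 10.1.1, the indication for whole-breast radiotherapy, which presupposes a first re-excision at <2 mm: "Patients with margins that are margins < 2 mm after reexcision for <2 mm margins, or, DCIS > 5 cm".

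The decision rules name no width. The interim rule in 13.1.1 reads "If 7 or more of the initial 25 needed re-excision, then the study will terminate". The final rule applies "If 18 or more of the initial 79 needed re-excision". Section 13.1.3 adds that "as soon as 18 patients require an additional surgical procedure, the study will be terminated". Section 13.2 speaks only of inadequate margins or any other reason.

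The 15% and 30% limits in section 2.1 follow directly on a local benchmark ("At USC, the re-excision rate for DCIS is about 20" per cent). Section 13.0 gives a figure of about 20% for margins under 1 mm in current practice at the centre.

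**The concern.** A patient whose closest margin is, say, 1.5 mm after immediate IORT is to be advised re-excision under 7.2.2, so on a plain reading of 13.1.1 she needed it. Under 10.1 re-operation is not indicated for her. No section says which rule governs the count.

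The count drives a binding stop at 25 patients, termination at 18 events, and the final conclusion. Widths are measured in every direction under 9.3, so both counts would be available at each look, and the choice could be made after seeing the data.

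Neither reading is clean. Counting at <1 mm leaves out of a re-operation endpoint some re-operations that the protocol itself advises. Counting at <2 mm appears to put the data on a different scale from the benchmark that introduces the limits. The treating surgeon also has conflicting instructions about a second operation.

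**Working it through.** **Step 1. Same patients, same time point?** Yes. Both 10.1 and 7.2.2 concern margins after wide local excision with immediate IORT. The anterior/posterior exception (9.3, and 13.0 for current practice) settles which margins matter, not how wide they must be, so it does not resolve the conflict.

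**Step 2. Reproduce the stated design.** Inputs from 2.1 and 13.1.1: acceptable re-excision rate 15%, unacceptable 30%, alpha 5%, beta 10%; continue with at most 6 failures in 25; positive conclusion with at most 17 failures in 79. With X1 ~ Bin(25, q) and X2 ~ Bin(54, q):

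- P(stop at 25) = P(X1 ≥ 7)
- P(go) = Σ over k = 0 to 6 of P(X1 = k) × P(X2 ≤ 17 − k)

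At q = 0.30, P(go) = 0.049, the type I error. At q = 0.15, P(go) = 0.904, the power. A search for the Simon optimal design with these inputs returns the same 25/79 design. The arithmetic is correct; what is unsettled is the event to be counted. The stop at 18 does not change P(go), because 18 failures already rule out a positive conclusion.

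**Step 3. Effect of the threshold.** Let q be the rate at <1 mm and d the share with margins from 1 to <2 mm. The documents do not give d, so it is assumed. Counting at <2 mm replaces q by q + d. Patients failing at <1 mm are a subset of those failing at <2 mm, so a positive conclusion at <2 mm implies one at <1 mm, and

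P(opposite conclusions on the same patients) = P(go at q) − P(go at q + d).

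With q = 0.15:

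| d (points) | P(stop at 25) | P(go) | P(opposite conclusions) |
|---|---|---|---|
| 0 | 0.070 | 0.904 | – |
| 1 | 0.092 | 0.864 | 0.040 |
| 2 | 0.118 | 0.814 | 0.090 |
| 5 | 0.220 | 0.609 | 0.295 |
| 10 (deliberately high) | 0.439 | 0.238 | 0.666 |

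For example, at d = 5: 0.9041 − 0.6094 = 0.2947.

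P(go) falls to 0.80 at a failure rate of 0.1725, that is d ≈ 2.25 points, or 0.0225 × 79 ≈ 1.8 patients. The 0.80 mark is only a reference point; the plan's own target is 0.90.

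**Step 4. Other base rates.**

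- q = 0.10: P(go) is 0.990. It is 0.972 with d = 2 (difference 0.018) and 0.904 with d = 5 (difference 0.086).
- q = 0.20, the centre's current figure: P(go) is 0.609. It is 0.238 with d = 5 (difference 0.371) and 0.049 with d = 10 (difference 0.560).

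**The case against.** The strongest reply is that <1 mm governs the count. Section 10.1 is the endpoint section, 13.0 opens the statistical section with a <1 mm description, and the Van Nuys index in Appendix 2 also uses <1 mm as its worst margin category. Only 7.2.2 is a direct rival rule: 5.3.4 concerns further therapy in general, and 10.1.1 is a radiotherapy indication that mentions <2 mm re-excision in passing. This is fair as to weight, but it does not remove the conflict. Section 13.0 describes current practice at the centre, whereas 7.2.2 prescribes what is done in this trial, and the re-operations it advises are the ones the rules would naturally count.

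The numerical effect is also assumed. The share in the 1 to <2 mm band is unknown, and a base rate of exactly 15% sits where P(go) falls steeply; at 10% the differences are much smaller (step 4). That the 15% and 30% limits were set at <1 mm is itself an inference, since 2.1 gives no width. These points stand and make the figures conditional. They do not touch the contradiction, which needs no calculation.

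Finally, this is a single-arm pilot and both counts could be reported. Reporting both still does not say which one stops the trial.

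**Conclusion.** The concern holds. The plan states two conflicting rules for when the primary event occurs, and nothing in it settles which one feeds the 7/25, 18/79 and stop-at-18 rules. This needs correcting before the rules can be applied. The design and its error rates reproduce and are not in question.

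The size depends on two quantities that the documents do not give: the true <1 mm rate in the trial and the share with 1 to <2 mm margins. At a <1 mm rate of 15%, the chance that the two counts lead to opposite conclusions runs from 0.04 with 1 extra point to about 0.29 with 5. At 10% it is about 0.09 with 5 extra points, and at 20% about 0.37. If the limits were set at <1 mm, as the 20% figure suggests, and events accrue as 7.2.2 generates them, the trial is more likely to stop or fail than planned.

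**What to change.** Have the clinical team choose one threshold, X mm, and use it in 5.3.4, 7.2.2, 10.1 and 10.1.1, with the anterior/posterior rule in 9.3. In 13.1.1 and 13.1.3, define the counted event by it. Suggested wording:

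> A patient counts as a failure if any margin of the initial excision is below X mm after applying 9.3, so that re-excision or mastectomy is indicated, whether or not it is performed. A lesion >5 cm with all margins at or above X mm [does / does not] count.

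The second sentence closes a related gap: 7.2.1 offers mastectomy as an alternative to whole-breast radiotherapy for such lesions, while 13.1 frames the primary aim by margins alone.

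Confirm that the 15% and 30% limits apply at X mm. Label the 20% benchmark as a <1 mm figure, or restate it at X mm if the centre's data allow. Report the count at the other threshold as a sensitivity analysis.

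The cost is protocol wording, with no added patients or procedures. The 25/79 cut-offs need recalculating only if the limits change. If <2 mm is chosen, the historical benchmark may look less favourable, and the documents do not say whether a <2 mm figure can be obtained from the centre's records.
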